A comparison of Mepitel Ag vs antibiotic ointment when used with a soft cast technique for the treatment of pediatric hand and foot burns, a prospective study

Protocol #: 15-1828

April 8, 2016

COMIRB Protocol

COLORADO MULTIPLE INSTITUTIONAL REVIEWBOARD
[name] [contact] [contact]

Protocol #: 15-1828

Project Title: A comparison of Mepitel Ag vs antibiotic ointment when used with a soft cast technique for the treatment of pediatric hand and foot burns, a prospective study

Principal Investigator: [name], MD

Version Date: 3/30/16

- I. **Hypotheses:** Mepitel Ag in combination with the soft cast technique improves wound healing in pediatric partial to deep partial thickness hand and foot burns by decreasing the length of healing time, decreasing the risk of yeast infection, and decreasing pain associated with multiple dressing changes.
- II. **Specific Aims:**
 - 1) To examine the efficacy of Mepitel Ag for use in pediatric partial to deep partial thickness hand and foot burns.
 - 2) To evaluate Mepitel Ag to triple antibiotic ointment when used in combination with a soft cast technique comparing healing time, yeast infection rates and pain levels at time of dressing change.

II. Background and Significance:

There is currently no gold standard dressing when it comes to treating hand or foot burns, specifically in the pediatric population. Our institution currently utilizes a soft cast technique (SCT) on all of our hand and foot burns. The SCT provides optimal positioning of the wounded hand or foot, allows for a moist wound environment, and offers protection of the injured extremity as the wound heals. Our current SCT uses triple antibiotic ointment (TAO) impregnated Adaptic gauze, kling or kerlex, cast padding, gypsoma plaster, soft cast material, and coban. This dressing is applied two to three times during the first 2 weeks post injury. To reduce the risk of the development of yeast overgrowth, the underlying dressing is changed to nystatin impregnated Adaptic gauze, kling or kerlex, cast padding, gypsoma plaster, soft cast material, and coban for the remainder of treatment time or until OR is indicated for surgical debridement and grafting of wounds..

A review of the current literature demonstrates silver sulfadiazine (SSD) to be the most frequently used dressing for burn wound treatment in many clinics nationwide.²⁸ The use of SSD is associated with once to twice daily painful dressing changes and wound exposure that "may lead to disruption of newly formed epithelium, wound colonization, subsequent wound infection and deepening of the burn".^{23, 28} One major benefit of the SCT is the reduction in

required dressing changes, as the soft cast can stay in place for 7-10 days while maintaining optimal hand or foot positioning. This eliminates the need for frequent painful dressing changes.

Occasionally, We have observed yeast infections when patients require serial casting and all have been treated with antibiotics. Other complications we have experienced include: occasional drying out of the adaptic gauze leading to a painful dressing removal and interruption of the newly epithelialized wound bed.

Mepitel Ag, a new soft silicone dressing produced by Molnlycke Health Care, combines Safetac technology with a silver compound to provide a broad spectrum of antimicrobial coverage. The safetac technology “protects the wound and the skin. It prevents an outer dressing from sticking to the wound, therefore minimizes trauma and pain”.¹⁵ The highly pliable nature and antimicrobial properties of the dressing make it an ideal alternative to TAO and SSD for the treatment of pediatric partial to deep partial thickness hand and foot burns. The silver compound lasts up to 8 days, while minimizing damage to the new epithelium and creating a moist wound environment. As Mepitel Ag is a relatively new product, there are currently no studies analyzing its efficacy and effectiveness when compared to other burn treatment methods.

The aim of this study is to compare Mepitel Ag to triple antibiotic ointment impregnated Adaptic gauze when used with the soft cast technique to assess overall time to healing, yeast infection rate and parents perception of pain level at time of dressing change on a scale of 1-10. The hypothesis is that Mepitel Ag in combination with the soft cast technique improves wound healing in pediatric partial to deep partial thickness hand and foot burns by decreasing the length of healing time, decreasing the risk of yeast infection, and decreasing pain associated with dressing changes.

III. Preliminary Studies/Progress Report:

A review of current literature found studies comparing SSD to other silver type dressings, SSD to Mepitel, and silver type dressings to topical antibiotic ointments. Search results failed to return articles on the soft cast technique for the treatment of burn wounds or the use or efficacy of Mepitel Ag. According to the literature, many silver containing products including SSD, Acticoat (silver rayon mesh), and Aquacel Ag (hydrofibre with silver ion) are indicated for partial to full thickness wounds, suggesting silver's ability to penetrate deeper burn injuries to promote wound healing.¹ Many studies found the silver type dressings to be associated with shorter healing time when compared to SSD and antibiotic impregnated gauze.

One important component of a burn dressing is “the creation of a moist wound-healing environment, the prevention of crust formation, and the physical protection of the wound against mechanical disturbances”.²⁸ In one review, antibiotic ointment impregnated gauze demonstrated adherence to the wound bed, causing damage to newly epithelialized cells during the dressing change.²⁸ In addition, Bacitracin, a component of TAO has been linked to promoting yeast colonization on healed wounds.⁷ Another study found yeast infections rates to be higher among children in the 1-16 year old age range, contributing this finding to “a higher sensitivity for Candida infections during childhood”.²⁰

Burn dressing changes have been reported as being some of the most traumatic and painful procedures for children.^{10, 23} In addition, daily dressing changes are rather time consuming and costly.²⁸ When determining acute burn wound care, it is important to utilize dressings that optimize wound healing while decreasing dressing frequency and subsequent patient pain. Mepitel, a grid like soft silicone coated nylon dressing that adheres only to intact skin, was found to demonstrate shorter wound healing time, less eschar formation, decreased pain, and lower cost when compared to SSD in one clinical trial.^{28,5} According to a study by Briggs et al, “silicone –based non-adherent dressings are especially beneficial in reducing pain during dressing changes in children.”³

This is due to the fact that “soft silicone dressing have been shown to prevent trauma to the wound bed and periwound skin and have been described as ‘atraumatic’”.¹⁴ Other benefits of soft silicone dressings include the ability to conform to anatomical contours, a reduction in scar development, and reduced overall cost secondary to improved wound healing and need for less frequent dressing changes.¹⁴

Mepitel Ag, a hybrid type soft silicone dressing impregnated with a silver compound was recently approved for use in partial thickness burns and partial and full thickness grafts.¹⁵ This combination of soft silicone and silver provides a relatively pain free dressing with broad spectrum antibiotic coverage. The aim of this study is to demonstrate that Mepitel Ag in combination with a soft cast technique is a superior alternative to antibiotic ointment impregnated gauze and soft cast for the treatment of pediatric hand and foot burns due to decreased healing time, decreased patient pain and lower yeast infection rates.

IV. Research Methods

A. Outcome Measure(s):

Primary outcomes utilized in this study include overall wound outcome, measured in length of days to re-epithelialization or need for surgical intervention, clinical assessment and wound progression photographs. Secondary outcomes include number of patients requiring surgical debridement, presence of infection based on odor, rash, deep red appearance or puritis. These wounds will not be cultured, patient pain level with dressing change based on the FLACC (Face, Legs, Activity, Cry, Consolability) scale, parents perceived level of pain, pain level at home based on family reported pain and pain medication use. We will also assess cost effectiveness of dressings including the number of clinic visits, number of soft casts, and the cost and amount of dressings used over the course of treatment.

B. Description of Population to be Enrolled:

Patients to be included in this study will be all Children's Hospital Colorado burn patients between the ages of 31 days and 18 years with newly diagnosed partial to deep partial or full thickness hand or foot burns, including bilateral or unilateral injury. Each injured extremity will serve as a separate data point. Exclusions include age > 18 years at start of study, silver allergy, silicone allergy, electrical or chemical burn, past medical history of immunodeficiency disorders such as diabetes mellitus, AIDs, or HIV, pregnant women, prisoners children under the protection of the department of human services, and the decisionally challenged.

C. Study Design and Research Methods

New burn clinic patients identified with a partial to deep partial or full thickness hand or foot burn will be randomized into either the Mepitel Ag group or the control group on their first clinic visit based on burn wound severity and age using RedCap. The randomization scheme in RedCap will be independently created by a statistician. Parental consent and or patient assent will be obtained prior to initial dressing. Burn severity will be clinically determined by one provider and one burn nurse during initial exam based on a 10 point burn severity classification scale in regards to the following parameters: 1) Superficial first degree- wound appears pink or red, involves epidermis only, no blisters present, dry; 2) Second degree, superficial partial thickness- burn involves epidermis + dermis, red or bright pink in color with blisters and or swelling, blanches, moist appearing; 3) Second degree, majority superficial partial thickness, minority superficial- burn involves majority ($\geq 66\%$) superficial partial thickness, epidermis + dermis, red or bright pink in color with blisters and or swelling, blanches, moist appearing, minority ($\sim 33\%$ or less) superficial first degree with areas of redness but no blistering; 4) Second degree, majority partial thickness, minority deep partial thickness- majority of burn ($\geq 66\%$) epidermis + dermis, red or bright pink in color, moist, less than half of burn ($\sim 33\%$ or less) is deep with pale pink-white areas, may or may not have a marbled or mosaic appearance; 5) Second degree, deep partial thickness- involves epidermis + dermis, pale pink to white in color, may have thin white moist eschar, may or may not have a marbled or mosaic type appearance, moist; 6) Second degree, majority deep partial thickness, minority superficial partial thickness- minority of burn ($\sim 33\%$ or less) involves epidermis + dermis, red or bright pink in color, moist, majority ($\geq 66\%$) of burn is deep with pale pink-white areas having a marbled or mosaic appearance, may or may not have thin white moist eschar, skin buds may or may not be present; 7) Second degree, deep partial thickness with areas of full thickness- majority of burn ($\geq 66\%$) involves epidermis + dermis, pale pink to white in color, may have thin white moist eschar, may or may not have a marbled or mosaic type appearance, moist, skin buds may or may not be present, minority of burn ($\sim 33\%$ or less) demonstrates thin to thick area of eschar white, brown or black in color, may need skin graft to heal; 8) Third degree full thickness with minority partial thickness- majority of burn ($\geq 66\%$) involves entire dermis + epidermis, thin to thick eschar that is white, brown or black in color, dry appearing, minority of burn ($\sim 33\%$ or less) is pink or red and moist, with blisters and or swelling, blanches; 9) Third degree full thickness- involves entire dermis + epidermis, thin to thick eschar that is white,

brown or black in color, dry appearing; 10) Fourth degree- third degree + muscle and or bone involvement. The provider and burn nurse will each give the patient a number and the severity will be determined based on the average of the 2 numbers. Any patient given a number 2, 3 or 4, will be placed into the "partial thickness" category, any patient given a 5, 6, or 7 will be placed into the "deep partial thickness" category, and lastly, any patient given an 8 or 9 will be placed into the "full thickness" category for burn severity.

Patients will be randomized into one of two groups, Mepitel Ag or standard TAO, using RedCap and based on a random clinical trial excel spread sheet balanced by burn severity. A statistician will provide a randomization scheme for investigators to follow. Photographs will be taken prior to dressing application at the initial visit and each subsequent visit. ~~Patient wounds will be dressed in either Mepitel Ag, kling or kerlex, cast padding, gypsoma plaster, soft cast material and coban for up to 21 days or until complete re-epithelialization of the wound occurs or unless surgery is indicated; the control, standard dressing of Triple Antibiotic Ointment impregnated adaptic gauze, kling or kerlex, cast padding, gypsoma plaster, soft cast material and coban for 10-14 days, or Nystatin impregnated adaptic, kling or kerlex, cast padding, gypsoma plaster, soft cast material and coban for 8-21 days or until complete re-epithelialization of the wound occurs or surgery is indicated. The SCT is applied by Occupational and Physical trained in casting and positioning. The soft cast provides optimal positioning while eliminating friction on the burn area. Dressing changes will occur every 3-10 days and will be determined by the provider, based on burn wound severity. Upon each return clinic visit, the patient will have their wound severity assessed by the following scoring system: 1=0% healed, 2=20% healed; 3=40% healed; 4=60% healed; 5=80% healed; 6=100% healed. This will be established by provider and burn nurse examination of the wound. This will be recorded in RedCap:_____~~

A member of the nursing team will also complete a questionnaire at each follow up visit to indicate pain level with dressing change based on the FLACC scale, parents perceived level of pain during dressing change, parental reported pain level at home, use of home pain medications, type of home pain medication- narcotic vs non-narcotic, clinical assessment of yeast rash including odor, visible rash, use of fluconazole, ease of dressing application, and amount and type of product used in dressing change.

D. Description, Risks and Justification of Procedures and Data Collection Tools:

A photography release will be distributed and signed by parent at initial visit.

Anursing questionnaire will be completed by nursing staff at each follow up appointment.

Local wound care including cleansing, wound measurement and dressing change will be performed by burn team including nursing staff and occupational and physical therapists. Although punch biopsy with histological analysis is considered the 'gold standard' in assessing burn wound depth, it is invasive and time consuming.¹⁸ Clinical assessment remains the most frequent and rapid method.¹⁸ Due to the time sensitive nature of the proposed trial and in order to avoid delaying wound care and initial dressing application, a 10 point clinical assessment scale has been created, as listed above for use in determining initial burn wound severity. Patient wound depth will be clinically determined by the average of the scores from the provider and the burn nurse.

The wound will also be assessed by the provider and nurse on subsequent visits using the following scoring tool: 1=0% healed, 2=20% healed; 3=40% healed; 4=60% healed; 5=80% healed; 6=100% healed. This will be established by provider and burn nurse examination of the wound. This will be recorded in RedCap.

The overall risk for this study is minimal, with no foreseen adverse reactions. The risk of a silver allergy or adverse reaction to silicone is very rare.

E. Potential Scientific Problems:

Limitations to the proposed study design include varying diagnostic opinions between provider and burn nurse for the determination of superficial vs deep partial thickness burn wounds based on clinical assessment, provider or nurse bias based on dressing preference, and possible uneven trial groups.

F. Data Analysis Plan:

Analysis Plan: Demographic and clinical characteristics will be summarized and compared between the two treatment groups using chi-squared and two-sample t-tests for categorical and continuous data, respectively. For analysis of the primary outcome, time to wound healing, we will use Kaplan-Meier curves, the log-rank test and a Cox proportional hazards model to determine the difference in days to re-epithelialization between the TAO and Mepitel Ag soft cast methods. Patients that require surgical intervention will be censored at the time of surgery. Logistic regression will be used to analyze the secondary outcomes, need for surgical debridement and occurrence of yeast infection. Pain level outcomes and pain medication use will be compared using two-sample t-tests and chi-squared tests. Cost effectiveness outcomes will also be analyzed.

1. Sample size: A statistical power analysis was performed to estimate power, based on results reported in A Soft casting Technique to Manage Pediatric Hand Burns: Less Pain, Greater Gain.²² Considering the simplest between group comparison and assuming a standard deviation of 0.3, alpha of 0.05 and 50 subjects per group there is over 90% power to detect a difference of 2 days between the treatment groups. Thus, we expect that our proposed sample size of 100 burns will be adequate for the main objective of this study.

G. Summarize Knowledge to be Gained:

To demonstrate that Mepitel Ag in combination with a soft cast technique improves wound healing in pediatric partial to deep partial thickness hand and foot burns by decreasing the length of healing time, decreasing the risk of yeast infection, and decreasing pain associated with dressing changes.

H. References:

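### Sections IV.A and IV.F give conflicting primary outcomes, and surgery is part of the primary measure in one, a censoring event in the other and a secondary outcome in both

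*Combined protocol and SAP*

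**What the plan says.** Section IV.A (Outcome Measure(s)) speaks of primary outcomes in the plural and describes them as "overall wound outcome, measured in length of days to re-epithelialization or need for surgical intervention, clinical assessment and wound progression photographs". It then adds: "Secondary outcomes include number of patients requiring surgical debridement".

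Section IV.F (Data Analysis Plan) speaks of one primary outcome: "For analysis of the primary outcome, time to wound healing, we will use Kaplan-Meier curves, the log-rank test and a Cox proportional hazards model", and the purpose of these methods is "to determine the difference in days to re-epithelialization between the TAO and Mepitel Ag soft cast methods". Its rule for surgery is: "Patients that require surgical intervention will be censored at the time of surgery". Surgery then returns as a secondary endpoint: "Logistic regression will be used to analyze the secondary outcomes, need for surgical debridement and occurrence of yeast infection".

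Section IV.F gives no analysis of clinical assessment or photographs as primary outcomes. Neither section ranks the primary measures or gives a multiplicity rule.

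**The concern.** A reader who follows IV.A and a reader who follows IV.F would analyse different primary outcomes. Surgery matters to the difference because it is a realistic outcome here: full-thickness burns are eligible (IV.B), and grade 7 of the severity scale in IV.C allows that a graft may be needed.

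Two things are at stake. First, on one natural reading of IV.A the day count stops at healing or at surgery, whichever comes first. A burn operated on at day 10 and a burn healed at day 10 then both score 10 days, although one is a failure of the dressing and the other a success. Second, where the primary outcome is not fixed, the deciding result can be chosen after data are seen. The plan describes no blinding, and IV.E itself names dressing preference among staff as a source of bias.

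**Working it through.** **1. The two sections side by side**

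| Item | IV.A | IV.F |
|---|---|---|
| Number of primary outcomes | Several | One |
| Surgery in the primary outcome | Inside the measure, role not explained | Censoring event |
| Surgery as a secondary outcome | Yes (number of patients) | Yes (logistic regression) |
| Clinical assessment, photographs | Listed as primary | No analysis given |

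The first, second and fourth rows disagree.

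**2. The plan's own figure.** The sample-size paragraph claims over 90% power for a 2-day difference, "assuming a standard deviation of 0.3, alpha of 0.05 and 50 subjects per group". The standard error is 0.3 × √(2/50) = 0.06 days, and 2/0.06 = 33.3 standard errors, so power is about 100%. The claim is true as an inequality. It is a comparison of means and does not say which definition of days it covers, so it does not settle the conflict. (The size of the standard deviation is a separate matter.)

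**3. Size of the artefact by arithmetic.** Assume IV.A is a time to the first of healing or surgery. If 10 percentage points more burns in one arm go to surgery about 10 days before they would have healed, that arm's mean falls by 0.10 × 10 = 1 day, half of the planned 2-day difference.

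**4. A small worked example (invented data, 50 per arm).** In each arm 20 burns heal on day 14 and 20 on day 17. The other 10 heal on day 24 in arm A and are operated on at day 10 in arm B.

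- Mean days with surgery counted as an end: A = (20×14 + 20×17 + 10×24)/50 = 17.2; B = (20×14 + 20×17 + 10×10)/50 = 14.4.
- Log-rank z = (O − E)/√V for arm B, where positive means faster:
  - Surgery as an event: O = 50, E = 5 + 17.78 + 16 = 38.78, z = +3.59.
  - Surgery censored (IV.F): O = 40, E = 17.78 + 16 = 33.78, z = +2.27.
  - Operated burns kept as unhealed: O = 40, E = 20 + 20 + 5 = 45, z = −1.52.

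The first two codings favour the arm in which 10 burns failed to heal without surgery. The third does not.

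**5. Simulation.** Assumptions, none from the documents: identical Weibull healing in both arms (mean 14 days, shape 3), operations on days 8–12, surgery in 10% of one arm and 20% or 25% of the other. There are 50 burns per arm, as planned. The table gives the share of trials in which the higher-surgery arm is significantly faster by log-rank (nominal 2.5% in that direction).

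| Burns operated on | Coding of surgery | 10% v 20% | 10% v 25% |
|---|---|---|---|
| Slowest to heal | Event (one reading of IV.A) | about 44% | about 61–72% |
| Slowest to heal | Censored (IV.F) | about 26–42% over both settings | |
| Slowest to heal | Kept as unhealed | 0.3% or less | 0.3% or less |
| Random | Event (one reading of IV.A) | about 6–7% over both settings | |

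The ranges reflect repeat runs and different ways of picking the slowest burns; one repeat of the random case gave 8–9%. In the slowest-burn rows the apparent gain under event coding is about 0.9–1.3 days. With equal surgery rates and the slowest burns picked by a common healing-time threshold, the event-coded rate was 1.7%, close to nominal.

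A second set of assumptions (gamma healing, mean 15 and SD 5 days; slowest burns operated on at day 10; 5% versus 20% surgery) gave 63%, 42% and 0% for event, censored and unhealed coding.

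**The case against.** The strongest reply is that IV.F already settles the matter. It names one primary outcome, specifies re-epithelialization as what is measured and states a rule for surgery. The hypothesis and aims also speak of healing time. On this view IV.A is loose wording. Much of this stands, and it limits what can be concluded:

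- A reader might infer that the planned test counts surgery as healing. It does not. The 44–72% belongs to a log-rank test on a combined endpoint that IV.F does not plan.
- A reader might take IV.A to be a combined endpoint beyond doubt. Its sentence can equally be a list: days to healing, and whether surgery was needed. On that reading early surgery does not shorten anything, but surgery is then both a primary and a secondary outcome.
- A reader might infer that the two definitions point in opposite directions. The checks do not show this. With unequal surgery rates and the slowest burns operated on, event coding and censoring differed in sign in only about 3–8% of runs, and in the worked example both favour the same arm. Only keeping operated burns as unhealed reverses the sign there.
- Clinical assessment and photographs may be meant as ways of judging healing, since IV.C and IV.D collect photographs and percent-healed scores at visits. IV.A nevertheless lists them under primary outcomes.

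The objection does not remove the conflict. IV.F does not say that it overrides IV.A, and the protocol never says which reading of IV.A is meant. Censoring also does not make surgery harmless: if the burns sent to surgery are the slow ones, censoring is informative and still favours the arm with more surgery.

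**Conclusion.** The contradiction is established from the text alone and needs no assumption: IV.A and IV.F cannot both define the primary outcome. Its numerical consequence is conditional on three things the documents do not give: that IV.A means time to the first event, that surgery rates differ between arms, and that slow burns are the ones operated on. With all three, at 10% versus 20–25% surgery, the false advantage is about 0.9–1.3 days and reaches significance in about 44–72% of trials. With surgical burns chosen at random, it reaches significance in about 6–7%. Selection in practice probably lies between these extremes. The documents give no surgery rates or timing, so no single figure can be claimed. The point is a should-fix: the wording decides which result counts as the trial's answer, and correcting it is cheap.

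**What to change.** - **IV.A:** replace the primary-outcome sentence with one outcome, time in days to complete re-epithelialization without surgery. Remove the need for surgery from it and keep surgery as a secondary outcome.
- **Healing scores and photographs:** describe the percent-healed scores and wound photographs as the means of judging healing, not as primary outcomes.
- **IV.F:** use the same definition and replace censoring at surgery. Treat surgery as a competing event, with operated burns kept in the analysis as unhealed: cumulative incidence of healing by arm, compared by Gray's test or a Fine–Gray model. Rewording IV.A alone is not enough, because censoring still gave about 26–42% false claims in the slowest-burn case. An arm with more surgery will then show less healing without surgery, which is what this outcome is meant to capture.
- **Sample size:** state that the 2-day difference refers to this outcome.

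The cost is a protocol amendment to two paragraphs, made before any comparison of outcomes by arm. It needs no extra patients and no new data beyond the healing and surgery dates that IV.F already requires.

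### No pain measure is named as deciding the pain hypothesis, and one behavioural scale serves ages 31 days to 18 years with no child asked to rate their own pain

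*Combined protocol and SAP*

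**What the plan says.** Reduced pain is one of the three benefits in the Hypotheses. The numbered Specific Aims mention it without a scale or a rater: "comparing healing time, yeast infection rates and pain levels at time of dressing change". The aim statement at the end of Background and Significance is more specific and names one measure only, "parents perception of pain level at time of dressing change on a scale of 1-10".

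Section IV.A lists four pain outcomes, all secondary. The first is "patient pain level with dressing change based on the FLACC (Face, Legs, Activity, Cry, Consolability) scale". The same sentence then adds "parents perceived level of pain, pain level at home based on family reported pain and pain medication use".

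In IV.C the data come from one form: "A member of the nursing team will also complete a questionnaire at each follow up visit". Its pain ratings are "pain level with dressing change based on the FLACC scale, parents perceived level of pain during dressing change, parental reported pain level at home", and it also records home pain medication. No item asks the child.

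Section IV.B enrols patients "between the ages of 31 days and 18 years", and the same pain measures apply to all of them. Section IV.F compares pain outcomes and medication use by t-tests and chi-squared tests. It names no lead measure, no visit, no way to combine repeated visits and no multiplicity rule.

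**The concern.** Two measures describe the same event, the dressing change, and the plan ranks neither above the other. If FLACC favours one arm and the parent rating does not, or the reverse, nothing says whether the pain hypothesis was supported, and the favourable result could be the one reported.

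The second problem is who supplies the rating. FLACC, as the protocol spells it out, scores face, legs, activity, cry and consolability. A cooperative school-age child or adolescent can be in pain without crying, kicking or needing to be consoled. The parent rating is a proxy as well. No masking is described, and IV.E concedes that providers or nurses may favour one dressing. A child old enough to describe the pain contributes no rating to a comparison that is partly about that pain.

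**Working it through.** **1. The plan's own figure.** The only power statement (IV.F) concerns healing time: difference 2 days, SD 0.3, alpha 0.05, 50 per group. Standard error = 0.3 × √(2/50) = 0.06, and 2 / 0.06 = 33.3 standard errors, so power is 1.000. The stated value of over 90% is literally true, but it does not concern pain. The documents give no pain effect size and no pain SD.

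**2. The sections side by side.**

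- Specific Aims: pain at dressing change, no scale, no rater.
- Background: parent rating, 1-10, no anchors; FLACC not mentioned.
- IV.A: FLACC, parent rating (no range), home pain, medication use; no order of importance.
- IV.C: FLACC and parent rating (no range) both recorded at each follow-up visit, with home pain and medication use.
- IV.F: all compared, none leading.

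The parent rating appears in the Background, IV.A and IV.C. It was not dropped in favour of FLACC. What is missing is a ranking, a range and anchors for the parent scale, and a rule for repeated visits.

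**3. Raters and ages.** FLACC is recorded by nursing staff, and the dressing-change and home ratings otherwise come from the parent or family. IV.C provides for patient assent, so the plan itself expects some children who can express a view. IV.C says randomisation uses severity and age, but its next paragraph mentions balance by severity only, and no age groups are defined. No existing cut-off can therefore be borrowed.

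**4. False positives without a lead measure.** For k independent tests at 0.05, the chance of at least one false positive is 1 − 0.95^k:

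- k = 2 (FLACC and parent rating): 1 − 0.9025 = 9.75%
- k = 3 (adding home pain): 14.3%
- k = 4 (adding medication use): 18.5%

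The two dressing-change ratings describe the same child at the same moment, so positive correlation is expected and the true figures would be lower.

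**5. What the planned size could show on pain.** With 50 independent burns per group and two-sided alpha 0.05, the detectable difference is (1.960 + z) × √(2/50) SDs:

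- 80% power: (1.960 + 0.842) × 0.2 = 0.56 SD
- 90% power: (1.960 + 1.282) × 0.2 = 0.65 SD

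Over an assumed SD of 1.5 to 3 points, this is 0.84 to 1.68 points at 80% and 0.97 to 1.94 points at 90%. The SD range is an assumption. Burns from the same child would not be independent, which these figures ignore.

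**The case against.** Pain is a secondary outcome, and several pain measures without a ranking is common in a small single-centre study. The parent rating does not share FLACC's item content, so the pain claim does not rest on FLACC alone. Self-report would not be blind either, since a child old enough to rate pain can see the dressing. All of this is fair. It limits the weight of the point but does not remove it: the hypothesis still has no deciding measure, and the child's own rating is still absent.

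Four stronger readings are tempting and are not supported:

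- *The aims and outcomes contradict each other.* A reader might infer that the parent score was replaced by FLACC. It was kept beside it, and the numbered Specific Aims name no scale at all.
- *FLACC is shown to be unsuitable for older children.* The documents give no validated age range and no data on how the scale behaves at its floor. The concern is reasoned from the items' content.
- *The dilution can be sized.* If a fraction q of children scored at the floor in both arms, and the rest responded in full, the observed mean difference would be (1 − q) of the true one. The documents supply neither q nor a pain difference; the 2 in the power statement is days of healing.
- *A parent scale starting at 1 biases the result.* Both arms use the same scale, so this alone does not bias the comparison. No anchors are given, so 1 might be labelled as no pain. The effect is an unclear scale.

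**Conclusion.** The point holds as a cheap improvement to a secondary outcome. The plan tests one of its three hypothesised benefits through nurse and parent ratings only, with no masking described and no measure named as decisive. It applies one behavioural scale across the whole age range without justification or self-report.

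The multiplicity cost for the two dressing-change measures is 9.75% under independence and lower under the positive correlation to be expected. The loss of sensitivity in older children cannot be quantified, because the age mix, the pain effect and the pain SD are not given. The healing-time analysis is unaffected.

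**What to change.** 1. Add one item to the nursing questionnaire in IV.C: the child's own 0-10 pain rating at the same dressing change, for children at or above a pre-stated age. Write the cut-off into the protocol. If the randomisation scheme does use age groups, state them and align the cut-off with them.
2. Name one lead dressing-change pain outcome, in the same words, in the Background aim statement, IV.A and IV.F: self-report at or above the cut-off, FLACC below it.
3. In IV.F, compare arms within each age group and then combine, for example as standardised differences with inverse-variance weights. State the visit used, or how repeated visits are summarised for each child.
4. Label parent-perceived pain, home pain and medication use as supportive. Give the parent scale one stated range, with anchors that include no pain.

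The cost is one extra question, a scale label and a few sentences, with no added procedure or staff. The downside is two instruments, so results are combined across age groups and not pooled as raw scores. Self-report adds the child's direct experience but does not cure the lack of masking, which the report should acknowledge.
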